# 4.3 Interim analyses and data monitoring

No interim analysis is planned for this study.

An external, independent Data Monitoring Committee (DMC) will monitor unblinded safety and efficacy data on an ongoing basis throughout the study. DMC members will have access to treatment assignments if knowledge of treatment assignment at the individual level is essential to evaluate safety. To minimize the potential introduction of bias, these individuals will not have direct contact with the study site personnel or subjects. An independent statistical service provider will generate unblinded reports for review by the DMC. If at any time there are safety concerns, the DMC will communicate the concerns to a representative from UCB senior management. The actual dates and the conduct of the DMC meetings are outlined in the DMC Charter.

# 4.4 Multicenter studies

For the purpose of the summaries and analyses, the term 'Site' will be used to define each center. The primary efficacy variable will be presented by treatment groups and region to explore interactions between treatment and regions according to Section 3.7.

# 4.5 Multiple comparisons/multiplicity

For addressing multiplicity issues, a hierarchical testing procedure will be implemented which consists of 3 steps.

- (1) Lumbar spine BMD percent change from Baseline at 6 months
- (2) Total hip BMD percent change from Baseline at 6 months
- (3) Femoral neck BMD percent change from Baseline at 6 months

The statistical test of the treatment effects in the second step will be made in a confirmatory manner only when the treatment effect on the primary efficacy endpoint is statistically significant using a 2-sided type I error rate of 0.05. Likewise, the third step will be made only when the treatment effect tested in step1 and step 2 are statistically significant using a 2-sided type I error rate of 0.05.

# 4.6 Examination of subgroups

To assess the consistency and robustness of the treatment effect on lumbar spine BMD, the primary analysis and selected secondary analyses will be performed for the following subgroups:

- age group (< 75 years,  $\ge 75$  years)
- region defined in section 3.7 (South, East, and North China)
- Baseline lumbar spine BMD T-score ( $\le$  -3, > -3 and  $\le$  -2.5, > -2.5; for lumbar spine BMD analysis only)
- Baseline total hip BMD T-score ( $\leq$  -3, > -3 and  $\leq$  -2.5, > -2.5; for total hip BMD analysis only)
- Baseline femoral neck BMD T-score ( $\leq$  -3, > -3 and  $\leq$  -2.5, > -2.5; for femoral neck BMD analysis only)
- Baseline Vitamin D (≤ 40 ng/mL, > 40 ng/mL) and loading dose of vitamin D (Yes, No)

Confidential Page 26 of 89

# 5 STUDY POPULATION CHARACTERISTICS

# 5.1 Subject disposition

The numbers and percentages of subjects who were screened with screen failure reason for the ES. The number of subjects who did not meet study eligibility criteria will be listed for the ES.

The numbers and percentages of subjects that were randomized, completed, prematurely discontinued from IMP, withdraw from study, reason for premature discontinuation from IMP and study, and successfully completing IMP and study will be summarized by the treatment groups and study periods (through Month 6, through OL period, Safety follow-up period, and through Month 15) for the RS. The number of subjects who completed each visit (as captured in the CRF) will also be listed. The number of subjects who withdrawal due to AE will be summarized and listed for the RS. In addition, the disposition of subjects into treatments groups and analysis sets (RS, FAS, SS, and PPS) will also be summarized on the RS.

# 5.2 Protocol deviations

Important protocol deviations (IPD) will be identified at data cleaning meetings (DCMs) prior to taking a snapshot from the database for the analysis. The identified important protocol deviations will be classified by predefined items (eg., inclusion criteria, exclusion criteria, incorrect treatment, prohibited medication, treatment non-compliance and procedural non-compliance) and summarized by the treatment groups and study periods for the RS. In addition, the number of subjects with at least 1 IPD will be displayed by site.

IPD related to COVID-19 protocol deviations will be summarized for treatment non-compliance and procedural non-compliance.

# 5.3 Impact of COVID-19

A summary table of visits and reasons affected by COVID-19 will be presented based on the Randomized set.

# 6 DEMOGRAPHICS AND OTHER BASELINE CHARACTERISTICS

The demographics and other Baseline characteristics will be summarized descriptively based on FAS. In case FAS and SS are different, the demographics will also be summarized based on SS.

# 6.1 Demographics

The continuous demographic variables:

- Age at study entry (years)
- Weight (kg)
- Height (cm)
- BMI (kg/m^2)

BMI (kg/m²) will be calculated as:

Confidential Page 27 of 89

$$BMI = \frac{\text{Weight (kg)}}{(\text{Height (m)})^2}$$

The categorical demographic variables:

- Gender
- Race
- Ethnicity
- Region
- Country
- EudraCT age categories (18-<65, 65 to <85, and  $\ge85$ )
- Marketing authorization ariations thereof. Clinicaltrials.gov age categories ( $\leq$ 18, 19 to <65, and  $\geq$ 65)
- Age class (<65,  $\ge 65$  to <75, and  $\ge 75$ )
- Age class ( $<75, \ge 75$ )
- Age strata group from IVRS ( $<75, \ge 75$ )
- BMI (kg/m^2) (<18.5, 18.5 to <23, 23 to <27.5,  $\ge27.5$ )

### 6.2 Other Baseline disease characteristics

- BMD T-score at lumbar spine, total hip and femoral neck
- BMD T-score categories at lumbar spine ( $\leq$  -3.0, > -3.0 to < -2.5, and  $\geq$  -2.5), total hip ( $\leq$ -2.5 and > -2.5) and femoral neck ( $\leq -2.5$  and > -2.5)
- BMD (g/cm²) by machine type (Hologic vs. Lunar) at lumbar spine, total hip and femoral neck
- bone turnover markers (sCTX [ng/L], P1NP [ug/L])
- years since menopause (year)
- laboratory parameters [calcium corrected by albumin, phosphorus, creatinine, serum 25 hydroxy (OH) vitamin D level, thyroid-stimulating hormone (TSH), and intact parathyroid hormone (iPTH) Total cholesterol, low-density Lipoprotein (LDL), highdensity Lipoprotein (HDL), triglycerides]
- prior osteoporosis medication use (Yes, No)
- type of osteoporosis medication use (eg. oral bisphosphonate, IV bisphosphonate, denosumab, teriparatide (TPTD), parathyroid hormone (PTH), calcitonin, strontium, fluoride, hormone replacement therapy, traditional herbal medication, activated vitamin D, SERM, vitamin K, other)
- Loading dose of vitamin D (Yes, No)
- Baseline use of calcium (Yes, No)

- 10 year probability of major osteoporotic and hip fractures based on WHO risk factor criteria (FRAX, see in Appendix 13.3) calculated with femoral neck BMD T-score
- oft any marketing authorization of any marketing thereof. 10 year probability of major osteoporotic and hip fractures based on WHO risk factor criteria (FRAX) calculated without femoral neck BMD T-score
- parental hip fracture (Yes, No, Unknown)
- glucocorticoid use (Yes, No)
- secondary osteoporosis (Yes, No)
- rheumatoid arthritis (Yes, No)
- alcohol use (Yes, No, Unknown)
- tobacco (Yes, No, Unknown)
- caffeinated beverage use (Yes, No, Unknown)

### 6.2.1 Cardiovascular risk factors:

- history of diabetes (type1, type2, No, Unknown)
- history of hypertension (Yes, No, Unknown)
- history of hyperlipidemia
- history of hypercholesterolemia (Yes, No)
- history of renal impairment (Yes, No, Unknown
- history of atherosclerosis (Yes, No, Unknown)
- prior heart failure (Yes, No, Unknown)
- prior transient ischaemic attack (Yes, No, Unknown)
- prior angina pectoris (Yes, No, Unknown)
- other prior cardiovascular ischaemic events (Yes, No, Unknown)

### Medical history and concomitant diseases 6.3

Previous and ongoing medical history will be summarized by MedDRA® SOC and PT. Medical procedures are not coded. The analysis will be performed based on FAS.

Prior fracture profiles will be summarized:

- fracture history (Yes, No, Unknown)
- prevalent vertebral fracture as assessed by the central imaging vendor based on the lateral spine x-ray (Yes, No, Unknown)
- number of prevalent vertebral fractures  $(0, 1, 2, \ge 3, \text{ not readable/missing})$  and incidences of the grade of prevalent vertebral fracture (SQ0, SQ1, SQ2, SQ3)
- historical fracture at or after age of 45 (Any historical fracture, historical osteoporotic fracture, historical nonvertebral fracture, historical major nonvertebral fracture)

Confidential Page 29 of 89

- historical fracture at or after age of 55 (Any historical fracture, historical osteoporotic fracture, historical nonvertebral fracture, historical major nonvertebral fracture)
- time since the most recent fracture (years)
- time since the most recent fracture ( $< 12 \text{ months}, \ge 12 \text{ months}$ )

### 6.3.1 Prevalent vertebral fracture

A subject has a prevalent vertebral fracture if any vertebra from T4 to L4 has a grade of  $\geq 1$  at baseline assessed by the central imaging vendor based on the lateral spine x-ray. A subject does not have a prevalent vertebral fracture when all 13 grades from T4 to L4 are 0. Otherwise, the subject will have an unknown status for prevalent vertebral fracture.

### 6.3.2 Any historical fracture

Any Historical fracture is defined as any fracture recorded on the Subject Fracture History eCRF regardless of trauma severity or vertebral fracture based on baseline spinal radiograph.

### Historical osteoporotic fracture 6.3.3

Historical osteoporotic fracture is defined as any nonvertebral fracture recorded on the Subject Fracture History eCRF not including skull, facial bones, fingers, toes, spine and tailbone and not associated with known high trauma severity or pathologic fractures, or vertebral fracture based on baseline spinal radiograph

### 6.3.4 Historical nonvertebral fracture

Historical nonvertebral fracture is defined as any fracture recorded on the Subject Fracture History eCRF not including skull, facial bones, fingers, toes, spine, and tailbone and not associated with known high trauma severity or pathologic fractures

### Historical major nonvertebral fracture 6.3.5

A subset of historical nonvertebral fractures including the following locations: pelvis (not hip), hip, lower leg (not knee or ankle), ribs, shoulder, forearm, and wrist and not associated with known high trauma severity or pathologic fractures

### Prior and concomitant medications 6.4

Prior medications include any medications that started prior to the start date of IMP. Past medications are a subset of prior medications, and include prior medications with a stop date before the date of first dose of IMP. Any treatment other than IMP administered from the time of signing the ICF to the EOS Visit will be considered concomitant medication. This includes medications that were started before the study and are ongoing during the study. If study medications with missing start date and end date without ongoing status, the medications will regard as both prior and concomitant medication. The analysis will be performed based on Randomized Set.

Medications will be summarized by WHO Anatomical Therapeutic Chemical (ATC) Classification, presenting Anatomical Main Group (ATC Level 1), Pharmacological Subgroup (ATC level 3), and preferred term.

UCB Statistical Analysis Plan

# 7 MEASUREMENTS OF TREATMENT COMPLIANCE

The IMP will be administered at the study site by staff trained in the injection technique. Date and time of IMP administration during double-blind period and open-label period will be recorded in the subject's eCRF.

Drug accountability must be recorded on the Drug Accountability form.

The expected day of administration will be based upon (1) the date of first IMP administration and (2) the previous injection date. The sum of the absolute difference in days between the actual and expected days will be summarized. In addition, a ratio of compliance will be computed based upon the actual and expected days for each of the 2 methods. The ratios of compliance will also be summarized as a continuous variable and categorically (<80% and  $\ge80\%$ ). The general formula for the compliance ratio is given as follows for double-blind period and overall period:

Compliance Ratio (CR) during double-blind period= {[Study Duration (days) during double-blind period] - [Cumulative Difference (days) during double-blind]} ÷ {Study Duration (days) during double-blind period}

Compliance Ratio (CR) during overall period = {[Study Duration (days) during Romosozumab treatment period] - [Cumulative Difference (days) during Romosozumab treatment period]} ÷ {Study Duration (days) during Romosozumab treatment period}

Compliance will be summarized as the number of doses received relative to the number of doses expected. Percent compliance will be calculated as:

Percent compliance during double-blind period = 100 x number of doses received during double-blind period  $\div$  number expected during double-blind period.

Percent compliance during overall period = 100 x number of doses received during Romosozumab treatment period = number expected during Romosozumab treatment period.

Treatment compliance will be presented for SS.

# 8 EFFICACY ANALYSES

The BMD efficacy analyses will be performed based on the FAS. The results from the central imaging vendor will be used in the FAS. PPS will also be utilized for sensitivity analyses. Statistical testing will be conducted as outlined in Section 4.5. For all confirmatory testing, both adjusted and unadjusted p-values will be provided. The derivation rules for the adjusted p-values are provided in Appendix 13.2. For each efficacy BMD endpoint, descriptive statistics will be provided for absolute values, change from baseline and percent change from baseline at post-baseline visit by machine-type and visit. In addition, mean (±SE) plot by visit will be presented for primary endpoint and observed case.

# 8.1 Statistical analysis of the primary efficacy variable

# 8.1.1 Primary analysis of primary efficacy variable

Primary analysis of Primary efficacy endpoint

Estimands's attributes to be considered for the evaluation of the primary endpoint

(1) Target Population: Postmenopausal Chinese women with osteoporosis meet the inclusion and exclusion criteria

Confidential Page 31 of 89

- (2) Treatment: Romosozumab or PBO for 6 months
- (3) Endpoint: percentage change from baseline in BMD at lumbar spine at end of DBPC period (month 6).
- (4) Intercurrent Events (ICEs) and strategies to handle ICEs:
  - (a) ICE #1: treatment discontinuation not due to COVID-19 will be handled by treatment policy strategy
  - (b) ICE #2: alternative osteoporosis therapy will be handled by treatment policy strategy.
  - (c) ICE #3: treatment interruption and impacted BMD data (missing or out of visit window) due to COVID-19 will be handled by hypothetical strategy
- (5) Population level outcome: difference of least square (LS) means for Romosozumab and PBO

ICE #1 Treatment discontinuation not due to COVID-19 and ICE#2 use of alternative osteoporosis therapy is rare (not expected to happen frequently). They will follow treatment policy strategy which align with ITT principle. The treatment policy strategy will include all available data observed at Month 6 regardless of the occurrence of intercurrent events. This means the analysis includes on- and off-treatment values collected after study participants prematurely discontinued study treatment but agreed to remain on the study and continued to attend visits and provide assessments at those visits or data after alternative/prohibited medication administrated. Those observed values will be analyzed according to the study participant's randomized treatment.

During COVID-19 pandemic, study procedures (i.e. IMP administration and BMD assessment) are heavily impacted by sites close, participants quarantined or partially lock down. Thus, treatment was interrupted, or BMD assessment could not be performed or performed out of window. Treatment interruption and impacted BMD data (missing or out of visit window) due to COVID-19 will be considered as ICE #3. Hypothetical strategy, in which the interest is in the treatment effect if the ICE did not occur, is a recommended option for most pandemic-related ICEs (R. Daniel Meyer, et al., 2020).

The data after ICE#1 and ICE#2 will be handled by treatment policy strategy and will use the observed data to do analysis. COVID-19 impacted data after ICE#3, then it will be setting to missing and imputed by multiple imputation (MI) under missing at random (MAR) assumption (MI-MAR). Details of this multiple imputation analysis are outlined in Appendix 13.4. This COVID-19 impacted data includes any BMD data after treatment interrupted (exceed 70 days since previous IMP, based on PK modeling which demonstrated that BMD loss begins after 70 days without dosing) and any missing data or out of window (exceed 70 days since previous IMP) data due to Covid-19 (other than actual COVID-19 infection). Missing data other than due to COVID-19 impacted will be imputed by LOCF.

Missing baseline BMD by DXA at any anatomical site will not be imputed and evaluated for the BMD analysis. Missing postbaseline BMD will be imputed using the LOCF approach (by carrying forward the last non-missing postbaseline value prior to the missing value from the same anatomical site) in the 6-month analysis.

In all visits and including the screening visit, if duplicated DXA assessment were performed on the same visit the mean of the duplicated BMD values will be used for analysis. The corresponding

Confidential Page 32 of 89

T-score at baseline will be converted using the mean of the duplicated BMD (checking missing DXA assessment during DEMs in section 4.2).

If a subject has BMD values from different DXA machine types (ie, Hologic and Lunar) only those BMD values that are collected from the same machine type as the Baseline BMD will be used for analyses and imputation. For anatomical sites that can be measured on different body sides (ie, left and right), only those BMD values that are collected from the same body side as the Baseline BMD will be used for analyses and imputation.

The comparison of the percent change from Baseline in lumbar spine DXA BMD at Month 6 between treatment groups will be evaluated using an analysis of covariance (ANCOVA) model. The ANCOVA model will include treatment group, age strata group (stratification factor), Baseline BMD value, machine type at baseline, region, and interaction of Baseline BMD value and machine type at baseline as independent variables. Summaries for the results will include least squares (LS) means point estimates of the percent change from Baseline for each treatment arm.. Summaries including the LS mean, standard error, 2-sided 95% CI and associated p-values (unadjusted p-value and adjusted p-value) will be provided for the difference between the LS means for romosozumab and placebo.

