13.4.1.1 Analysis of secondary variables

For the secondary efficacy BMD endpoints (at total hip and femoral neck at Month 6), a percent change from baseline in DXA BMD will employ an ANCOVA model. The ANCOVA model will include treatment group, baseline value of BMD, machine type at baseline and interaction of baseline BMD value and machine type at baseline as independent variables. Summaries of the results will include LS means point estimates of the percent change from baseline for each treatment arm. The variance structure will allow for heterogeneity between treatments. The 2-sided 95% CI and associated p-value will be provided for the difference between the LS means for romosozumab and placebo. The FAS will be used for these analyses.

A sensitivity analysis with a repeated measurements model will be fit with the percent change from baseline at Months 3 and 6 in BMD of the corresponding skeletal location (ie, total hip or femoral neck) as the dependent variable and baseline BMD, machine type, interaction of baseline BMD and machine type, visit (categorical), treatment (categorical), and interaction of treatment and visit as the independent variables. The variance structure will allow for heteroskedasticity of variance between treatment groups. Due to the sensitivity nature of this analysis, formal significance testing will not be conducted.

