# 2.6 Determination of sample size

The sample size calculations were done using historical BMD data of all 3 anatomical sites taken into account from the romosozumab studies 20070337 and 20120156.

• Assumptions for BMD of the lumbar spine:

Postmenopausal women with osteoporosis in 20120156 showed a treatment difference of 8.4 with 95% CI: 6.9 to 9.9 when compared with placebo BMD response at lumbar spine. Furthermore, postmenopausal women with osteoporosis in 20070337 showed a treatment difference of 9.4 (95% CI: 7.9 to 10.8). Taking the minimum of the lower confidence bound (conservative approach) results in an assumption of 6.9 for the treatment difference in percentage change from baseline at Month 6.

For postmenopausal women with osteoporosis in 20120156, the upper bounds of the SDs were 4.94 for the romosozumab group and 3.93 for the placebo group; in 20070337, the upper bounds of the SDs were 6.10 and 3.32, respectively. This indicates that SDs were differing between romosozumab and placebo necessitating a statistical test accounting for differing SDs. To merge the SDs of 20070337 and 20120156, the pooled common SDs were calculated separately for romosozumab and placebo taking the upper bound in each study and each arm (conservative approach). As a result, the assumptions for the SDs are 5.26 for the romosozumab arm and 3.34 for the placebo arm.

Assumptions for BMD of the total hip

Studies 20070337 and 20120156 showed a minimum treatment difference on total hip BMD of 3.5 (95% CI: 2.5 to 4.4) when compared with placebo. The combined upper bounds of the SDs for 20070337 and 20120156 were 3.80 for the romosozumab group and 3.03 for the placebo group.

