# 8.2.1 Secondary efficacy variables - DBPC Period

For the secondary efficacy BMD endpoints during the DBPC Period (at total hip and femoral neck at Month 6), a percent change from Baseline in DXA BMD will employ an ANCOVA model. The ANCOVA model will include the same independent variables and interactions as described in Section 8.1.1. The FAS will be used for this analysis. This analysis will be performed with adjustment for multiplicity as described in Section 4.5. Nominal (unadjusted) p-values will be provided as well for exploratory purposes.

A sensitivity analysis will be performed on the analysis of the secondary efficacy variable as described in the above paragraph based the PPS. In addition, a MMRM will be fit with the percent change from Baseline at Months 3 and 6 in BMD of the total hip and femoral neck with

the same independent variables and interactions as described in Section 8.1.1. The FAS will be used for these analyses.

For the secondary efficacy BMD endpoints at total hip and femoral neck, the following 2 further sensitivity analyses will be conducted:

Only those values are included in analysis, which were assessed during the period when subjects received IMP and does not apply to any alternative osteoporosis therapy (licensed drugs only). In particular, all values which were assessed more than 70 days after last dose of IMP or were assessed after the first intake of alternative osteoporosis therapy (licensed drugs only) will be considered as missing data and will not be imputed. For one analysis, missing data imputation via LOCF will be applied, and for the other analysis via multiple imputation according to missing at random assumption will be applied.

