/***** for intermittent missing values ******/
PROC MI data=xxx NIMPUTE = 100 seed=xxx NOPRINT OUT=xxxx min=0 max=1;

BY trtp;

VAR type agegp region1 region2 base aval_m3 aval_m6;

MCMC CHAIN=multiple IMPUTE = monotone;

run;

/******* for monotone missing values *********/
proc mi data=xxx seed=xxx nimpute=1 NOPRINT out=xxxx;
var agegp trtp region machinetype base aval m3 aval m6;
class agegp trtp region machinetype
MONOTONE REGRESSION
BY imputation;
run;
PROC MIXED DATA
         BY imputation
         CLASS trtp type region agegp;
         MODEL pchg=base trtp type agegp region base*type;
         LSMEANS trtp / om cl stderr pdiff;
       ods output LSMeans=LMS Diffs=DIFF;
 *** MIANALYZE;
proc sort data=DIFF; by imputation; run;
```

This document cannot be used any extensions of variations thereof.

Confidential

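### The primary ANCOVA makes no provision for unequal variances, although the sizing section says they must be allowed for; at 2:1 allocation the lumbar spine 95% CI comes out about 15% too wide

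*SAP*

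**What the plan says.** **Sizing.** SAP 2.6 (same text in protocol 13.8) compares the lumbar spine SDs of the two source studies and concludes: "This indicates that SDs were differing between romosozumab and placebo necessitating a statistical test accounting for differing SDs". It then sets the planning values: "As a result, the assumptions for the SDs are 5.26 for the romosozumab arm and 3.34 for the placebo arm". The power calculation uses a two-group Satterthwaite t-test with 2:1 allocation.

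**Primary analysis.** In SAP 8.1.1, "The ANCOVA model will include treatment group, age strata group (stratification factor), Baseline BMD value, machine type at baseline, region", together with the baseline-by-machine interaction. Protocol 13.4.1 has a similar model with fewer covariates. Neither says anything about the variance structure.

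**Secondary analysis.** For total hip and femoral neck, protocol 13.4.1.1 adds: "The variance structure will allow for heterogeneity between treatments". SAP 8.2.1 replaces this with: "The ANCOVA model will include the same independent variables and interactions as described in Section 8.1.1". Section 8.1.1 has no variance statement, so the provision is lost. SAP 3.9, which lists departures from the protocol's analyses, does not mention it.

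**Sensitivity analysis.** The repeated-measures model (protocol 13.4.1 and 13.4.1.1; SAP 8.1.2) does allow the variance to differ by arm.

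**Code.** The ANCOVA in SAP 13.4 is a PROC MIXED step with "MODEL pchg=base trtp type agegp region base*type" and no REPEATED / GROUP= statement. PROC MIXED then estimates a single residual variance. SAP 8.1.1 sends the primary imputation analysis to this appendix.

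**The concern.** The plan states that unequal SDs need a test that allows for them, and it makes that allowance everywhere except at the endpoint where its own SDs differ most. Followed as written, the primary ANCOVA is the default common-variance fit.

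Under equal allocation this would hardly matter. Here the larger arm also has the larger SD. Pooling in effect divides each arm's variance by the other arm's sample size, so the larger variance is divided by 100 instead of 200 and the standard error of the difference is overstated.

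What is at stake is the accuracy of the standard error, CI and p-value for the primary estimate and the two gatekept secondary estimates, and agreement between the test used for sizing and the test used for analysis. The study bridges to fracture data from elsewhere (protocol 5.4.2), so the size and precision of the BMD effect will be read, not only its significance. The variance structure also has to be fixed before unblinding: the review of assumptions in SAP 8.1.2 is blinded and cannot compare SDs by arm.

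**Working it through.** **1. Reproducing the plan's figure.** Femoral neck, difference 2.0 (lower confidence bound), SDs 4.39 and 4.10, 146 and 73 subjects, two-sided 5%, Satterthwaite test:

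- SE = √(4.39²/146 + 4.10²/73) = 0.602, df ≈ 153, power 91.0%.
- The smallest 2:1 sample giving 90% is 142 + 71.
- At the same size, power is 99.9% for total hip (difference 2.5) and above 99.9% for lumbar spine (6.9).

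The stated 146 + 73 for at least 90% power is confirmed.

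**2. Lumbar spine, 200 and 100 subjects, SDs 5.26 and 3.34.**

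- Unequal-variance SE = √(5.26²/200 + 3.34²/100) = √(0.1383 + 0.1116) = 0.500.
- Pooled variance = (199 × 5.26² + 99 × 3.34²)/298 = 22.18.
- Pooled SE = √(22.18 × (1/200 + 1/100)) = 0.577.
- Ratio of SEs = 0.5768/0.4999 = 1.154.
- 95% CI half-widths: 1.135 pooled, 0.984 unequal-variance.
- Coverage of the pooled interval = 2Φ(1.968 × 1.154) − 1 ≈ 97.7%, so the true two-sided error is about 2.3%.

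Since (0.4999/0.5768)² = 0.75, the pooled interval is as wide as a correctly computed one from a trial three-quarters the size.

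**3. All three sites at 200:100, same formulas.**

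| Site | SDs | Pooled SE | Unequal-variance SE | Ratio | Coverage |
|---|---|---|---|---|---|
| Lumbar spine | 5.26 / 3.34 | 0.577 | 0.500 | 1.154 | 97.7% |
| Total hip | 3.80 / 3.03 | 0.436 | 0.405 | 1.077 | 96.6% |
| Femoral neck | 4.39 / 4.10 | 0.526 | 0.514 | 1.023 | 95.6% |

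With 150 per arm the ratio is 1.00 at every site, so the effect comes from unequal allocation combined with unequal SDs.

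**4. Dependence on the planning SDs.** For study 20120156, "the upper bounds of the SDs were 4.94 for the romosozumab group and 3.93 for the placebo group"; those values give a ratio of 1.08. For the other study, "in 20070337, the upper bounds of the SDs were 6.10 and 3.32, respectively"; those give 1.20. The merged SDs do not share one weighting. On the variance scale, 5.26 implies a weight on 20070337 of (5.26² − 4.94²)/(6.10² − 4.94²) = 25%, while 3.34 implies (3.93² − 3.34²)/(3.93² − 3.32²) = 97%. Applying a common weight anywhere from 25% to 97% to both arms gives an excess width of 11% to 20%.

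**5. With covariates.** The eight-parameter ANCOVA was simulated 6,000 times at 200:100. The covariate distributions are assumptions: 20% in the older stratum, three equally likely regions, half on each machine type, normal baseline, and no covariate effects. The common-variance interval covered 97.7% with type I error 0.023, and its SE averaged 1.15 times a heteroscedasticity-robust SE. The robust interval covered 95.3%.

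**6. Arm-level intervals.** The code also requests confidence limits for each arm's LS mean. Ignoring covariates, the pooled SD is √22.18 = 4.71. The romosozumab SE becomes 4.71/√200 = 0.333 instead of 5.26/√200 = 0.372, about 10% too small (coverage about 92%). The placebo SE becomes 4.71/√100 = 0.471 instead of 0.334, about 41% too large. For single arms, then, pooling errs in both directions.

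**The case against.** **Equal variance is inferred, not stated.** This is true. SAP 8.1.1 is silent, and the code is labelled as pseudo-code for a sensitivity ANCOVA and is incomplete in places. But a programmer following an ANCOVA specification with no variance statement will fit the common-variance model. The only code available does the same, and the primary imputation analysis is sent to that appendix. The plan adds a variance statement where it wants one, which makes its absence here harder to read as an oversight in wording.

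**The 15% is conditional.** Also true. It rests on conservative upper-bound SDs that were merged inconsistently. The range is 8% to 20% across the source studies' own SDs, and the direction is the same throughout.

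**No decision changes.** This stands. At a difference of 6.9 the lumbar spine result is about 12 pooled standard errors from zero (6.9/0.577), and power exceeds 99.9% under either model. Femoral neck power at 200:100 and a difference of 2.0 is 96.7% pooled against 97.2%; at 146:73 it is 90.1% against 91.0%. Type I error stays below 5% and the testing hierarchy is safe.

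**An unequal-variance analysis is already planned.** The repeated-measures model will show whether pooling matters. However, it handles missing data differently, is not confirmatory, and does not correct the primary interval.

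**Sizing with a t-test and analysing with ANCOVA is ordinary practice.** Agreed. The inconsistency lies in declaring that unequal SDs must be accounted for and then not doing so.

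**Conclusion.** The concern holds. As written, the primary ANCOVA defaults to a common residual variance, contrary to the plan's own reasoning. The SAP also removes, without listing it, the protocol's provision for the two secondary endpoints.

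Under the plan's SDs and 200:100 allocation, the 95% CI for the treatment difference is about 15% too wide at the lumbar spine, 8% at the total hip and 2% at the femoral neck. These figures assume that the residual SDs keep the planning ratio and that covariates explain a similar share of variance in each arm.

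For the treatment differences the error is conservative and puts no efficacy conclusion at risk at the planned effect sizes. The matter is correct error bars and consistency within the plan. It should be changed, but it does not undermine the trial.

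**What to change.** - **SAP 8.1.1 and 8.2.1:** state that the ANCOVA has a separate residual variance for each treatment group, with Satterthwaite or Kenward-Roger degrees of freedom. This also restores the protocol's specification for total hip and femoral neck.
- **SAP 13.4 code:** add a REPEATED statement with GROUP=trtp and the matching DDFM option. Fit this model within each of the 100 imputed datasets before applying Rubin's rules.
- **SAP 3.9:** record the variance structure for the primary endpoint as a clarification of the protocol, which is silent there.

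A heteroscedasticity-robust standard error would be an acceptable alternative, since it restored coverage to 95.3% in the simulation. Either choice should be written into a SAP amendment before the 6-month data are unblinded. The cost is one sentence, one model statement and one extra variance parameter, which 300 subjects can easily support.
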